3. OBJECTIVES, ENDPOINTS AND ESTIMANDS

Table 4 Objectives and Endpoints

Objectives	Endpoints		
Primary			
To evaluate if Test Study Intervention (T): Albendazole tablets IP 400 mg, manufactured by Biddle Sawyer Limited is bioequivalent to Reference Study Intervention (R): Albendazole Tablets 400 mg, manufactured by GSK Consumer Healthcare, South Africa (PTY)	Albendazole Cmax and AUC(0-t)		
Secondary			
• To assess secondary pharmacokinetic parameters of Test Study Intervention (T): Albendazole tablets IP 400 mg relative to Reference Study Intervention (R): Albendazole tablets 400 mg.	 Albendazole AUC0-∞, Tmax, t1/2, lambda-z (λz) and AUC_%Extrap_obs. Albendazole sulfoxide Cmax, AUC(0-t), AUC0-∞, Tmax, t1/2, lambda-z (λz) and AUC_%Extrap_obs. 		
To assess the safety and tolerability of a single oral dose of the test versus the reference study intervention.	 Incidence of AE. Absolute and change from baseline in vital signs parameters at each timepoint. 		

Primary estimand/coprimary estimands

The primary clinical question of interest is:

To evaluate if Test Study Intervention (T): Albendazole tablets IP 400 mg is bioequivalent to Reference Study Intervention (R) Albendazole tablets 400 mg in healthy adult participants under fed conditions.

The estimand is described by the following attributes:

- **Population**: Healthy adult participants between 18 to 45 years of age.
- **Treatment condition**: Single dose of Albendazole tablets IP 400 or Albendazole tablets 400 mg, each treatment period given under fed conditions to healthy participants.
- Variable/endpoint: Cmax and AUC(0-t)

• Summary measure:

• Treatment ratios of geometric least square means with 90% CI, and within-subject coefficient of variation of reference study intervention (intra-subject CV in %).

Intercurrent events:

- Permanent Treatment discontinuation due to any reason (includes COVID-19 positive, AE related withdrawal etc.) While-on treatment strategy that is, all available data up until the withdrawal of the consent will be reported.
- ∘ Use of prohibited or rescue medication (Section 6.9) which could affect PK parameters (Cmax and AUC(0-t)) during the study Hypothetical strategy

Experiences emesis/vomiting before 2 times of median Tmax (i.e. 2 x 2hour = 4hour) after dose administration – Hypothetical strategy.

Rationale for estimand:

- The rationale of the while on treatment strategy is to estimate the PK parameters when participants have taken the dose/treatment condition.
- The rationale of hypothetical strategy for prohibited/rescue medication is to minimize the potential confounding of PK data (Cmax and AUC(0-t)). It attempts to estimate treatment effects had the intercurrent event not occurred. In this scenario, if the intercurrent event occurred before 2 times median Tmax (i.e. 2 x 2hour = 4hour) after study drug administration, PK parameters (Cmax and AUC(0-t)) data would be set to be missing for that period.
- Hypothetical strategy would be considered if emesis/vomits occur before 2 times the median Tmax (i.e. 2 x 2hour = 4hour) after study drug administration in particular period, this is because the drug would not have been absorbed into the body. In this situation, PK parameters (Cmax and AUC(0-t)) data would set to be missing for that period.

Secondary estimand(s) - PK endpoint

The secondary clinical question of interest is:

To assess secondary pharmacokinetic parameters of Test Study Investigation (T): Albendazole tablets IP 400 mg relative to Reference Study Investigation (R): Albendazole tablets 400 mg.

The estimand is described by the following attributes:

• **Population**: Healthy adult participants between 18 to 45 years of age.

• Treatment condition: Single dose of Albendazole tablets IP 400 mg or Albendazole tablets 400 mg, each treatment period given under fed conditions to healthy participants.

• Variable/endpoint:

- **Albendazole** AUC0-∞, Tmax, t1/2, λz and AUC_%Extrap_obs.
- Albendazole sulfoxide Cmax, AUC(0-t), AUC0-∞, Tmax, t1/2, λz and AUC %Extrap obs.

Summary measure:

Descriptive statistics (N, n, arithmetic mean, 95% CI of arithmetic mean, SD, median, minimum, maximum and geometric mean) will be presented for untransformed secondary PK parameters (AUC0- ∞ , AUC(0-t), Tmax, t1/2, λ z and AUC %Extrap obs).

• Intercurrent events:

Same as primary endpoint

• Rationale for estimand:

o The rationale of hypothetical strategy which is impacted to secondary PK parameters (AUC0-∞, AUC(0-t), Tmax, t1/2, λz and AUC_%Extrap_obs) during the study is same as primary estimands.

Secondary estimand(s) - 2(Safety)

The secondary clinical question of interest is:

To assess the safety and tolerability of a single oral dose of Test Study Intervention (T):

Albendazole tablets IP 400 mg relative to Reference Study Intervention (R): Albendazole tablets 400 mg.

The estimand is described by the following attributes:

- **Population**: Healthy adult participants between 18 to 45 years of age.
- Treatment condition: Single dose of Albendazole tablets IP 400 mg or Albendazole tablets 400 mg, each treatment period given under fed conditions for healthy participants.
- Variable/endpoint: Incidence of AE and Absolute and change from baseline in vital signs parameters at each timepoint.

• Summary measure:

• Number and percentage will be presented for incidence of AE.

• Descriptive statistics (N, n, mean, SD, median, minimum and maximum) will be presented for absolute and change from baseline values of vital signs parameters at each timepoint.

• Intercurrent events:

Permanent Treatment discontinuation due to any reason (includes COVID-19 positive, AE related withdrawal etc.) – Treatment policy strategy.

• Rationale for estimand:

Permanent Treatment discontinuation due to any reason will be handled with a treatment policy strategy as occurrence of AE until participant are on study will be collected and reported.

4. STUDY DESIGN

4.1. Overall design

Study Design:

An Open Label, Balanced, Randomized, Two-Treatment, Four-Period, Two-Sequence, Single Oral Dose, Full Replicate Crossover, Bioequivalence Study of Albendazole Tablets IP 400 mg of Biddle Sawyer Limited (GSK group company) with Albendazole Tablets 400 mg of GSK Consumer Healthcare, South Africa (PTY) Ltd in Healthy, Adult Participants under Fed Condition.

Housing:

Participants will be housed in the clinical facility at least 11 hours before administration of the intervention and will continue to remain in the clinical facility for at least 24 hours after administration of the intervention in each period.

The participants will have to stay in the facility for 2 consecutive nights in each period.

In case of any adverse event, necessary action will be taken till the event subsides.

Wash-out Period:

There will be a washout period of at least 7 days between dosing days of any 2 consecutive periods.

Dosing:

Dose administration as described below will be done under the supervision of trained study personnel.

After an overnight fast of at least 10 hours, participants will be served high fat high calorie vegetarian breakfast 30 minutes prior to dosing, which they are required to consume within 30 minutes (Section 5.3.1). Study Intervention will be administered to the participants while in sitting position with 240 ± 2 mL of drinking water at the ambient temperature in each period. The tablets should be swallowed whole without chewing or crushing.

This activity will be followed by a thorough mouth check with torch & disposable spatula by the trained study personnel immediately after study intervention administration to assess compliance to dosing. The time of administration of the study intervention will be the time

at which the participant completes drinking 240 ± 2 mL of water and that will be captured in the respective source data forms.

4.2. Scientific rationale for study design

The manufacturing of albendazole tablets is being transferred from Cape Town, South Africa to Nashik, India. To ensure appropriate exposure after administration of the newly produced tablets from India, bioequivalence is required to be proven between the tablets from both locations. Therefore, this study evaluates the bioequivalence between the Sponsor's test study intervention (albendazole 400 mg tablets from Nashik, India) with respect to the reference study intervention (albendazole 400 mg tablets from Cape Town, South Africa) in healthy adult participants under fed condition.

Albendazole is a molecule with high intra-subject variability supported from literature² and in-house experience. Additionally, as per WHO product specific guidance (Notes on the Design of Bioequivalence Study: Albendazole; 29 March 2021), albendazole PK in the fed state is highly variable (up to 68% for Cmax and 62% for AUC). The WHO guideline for albendazole bioequivalence studies strongly recommends a replicate cross-over study design for albendazole bioequivalence studies, to estimate intra-subject PK variability more accurately which allows to widen the acceptance range for Cmax and AUC(0-t) ratios. Given the large variability in albendazole and albendazole sulfoxide PK, such potential larger differences in Cmax and AUC(0-t) between the proposed product and the comparator that might be accepted due to the widened acceptance range are expected to lack clinical relevance. In line with the WHO product specific guidance document, this study implements a fully replicate 4-period study design.

The PK sampling and washout period of 7 days are designed to ensure that PK parameters will be well-estimated and pre-dose concentrations are negligible in each subsequent period.

Depending on the CV% in Cmax and AUC(0-t), a joint power calculation showed that 48 evaluable participants were required to achieve a joint power of at least 90% for the two primary endpoints. Taking into account an expected dropout with fully missing data in up to 30% of participants, a total of 70 healthy adult participants will be enrolled. In case of only partially missing data in those 30%, the joint power of this study may be over 90% (Section 9.6).

4.2.1. Participant input into design

4.3. Justification for dose

The average daily dose of albendazole is 400 mg up to 2 times a day. This is taken as one 400 mg tablet up to 2 times per day with a maximum dose of 800 mg per day.

This study will be assessing the bioequivalence of a single dose of Albendazole Tablets IP 400 mg or Albendazole Tablets 400 mg in each period under fed conditions, according to a 4-period, 2-sequence full replicate crossover design bioequivalence study with a washout period of 7 days.

4.4. End-of-study definition

A participant is considered to have completed the study if the participant has completed all periods of the study including the last scheduled procedure shown in the SoA (i.e. at the time of check-out of period IV).

Thus, the end of study will be the last scheduled procedure (blood collection for PK sample and safety assessment at the time of check-out of period IV) of the last participant in the study.

5. STUDY POPULATION

Prospective approval of protocol deviations to recruitment and enrollment criteria, also known as protocol waivers or exemptions, is not permitted.

5.1. Inclusion criteria

Participants are eligible to be included in the study only if all of the following criteria apply:

- a) Non-smoker, healthy, adult human participants between 18 to 45 years of age (both inclusive).
- b) Having a BMI between 18.5 to 30.0 (both inclusive), calculated as weight in kg/height in m².
- c) Not having any significant diseases or clinically significant abnormal findings during screening, medical history, clinical examination, laboratory evaluations, 12-lead ECG and X-ray chest (postero-anterior view) recordings.
- d) Able to understand and comply with the study procedures, in the opinion of the principal investigator.
- e) Able to give voluntary written informed consent for participation in the study.
- f) In case of female participants:
 - Surgically sterilized at least 6 months prior to study participation;

Or

If of childbearing potential is willing to use a suitable and effective double barrier contraceptive method or intra uterine device during the study.

And

Serum pregnancy test must be negative.

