2.2. Background

Albendazole is a benzimidazole carbamate with antiprotozoal and anthelmintic effects against intestinal and tissue parasites. Albendazole exhibits larvicidal, ovicidal and vermicidal activity, and it is thought to exert its anthelmintic effect by inhibiting tubulin polymerization. This causes the disruption of the helminth metabolism, including energy depletion, which immobilizes and then kills the susceptible helminth.

Pharmacokinetics:

In humans, albendazole is poorly absorbed (less than 5%) following oral administration, but its absorption is greatly enhanced (approximately 5-fold) when taken with fat-rich food. After absorption, albendazole rapidly undergoes extensive first-pass metabolism in the liver resulting in several metabolites of which albendazole sulfoxide is its main metabolite.

Peak concentrations are achieved for albendazole approximately 2 hours after dose, and for albendazole sulfoxide approximately 4 hours after dose. The $T_{1/2}$ of albendazole is approximately 1.5 hours and for albendazole sulfoxide 8.5 hours.

For gastro-intestinal infections, the parent compound albendazole is considered the active moiety, whereas for systemic infections this is albendazole sulfoxide. For the purpose of determining bioequivalence, however, the WHO requires this to be shown for the albendazole parent compound.

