2.3. Benefit/risk assessment

Participation in bioavailability studies yields no direct benefit to the participants. However, a charge-free study related health assessment is provided. The risks as described below are reduced considering the fact only 4 doses are to be administered at an interval of at least 7 days between dosing days of any 2 successive periods.

Table 3 Potential risks and risk mitigation strategies

The potential risks of clinical significance for albendazole tablets are derived from the prescribing information (Albendazole label). Most of these reported risks are uncommon, rare or very rare. The likelihood of these risks in a healthy population receiving a single dose is therefore expected to be low. For complete list of adverse reactions please refer the prescribing information mentioned above.

Potential Risk of Clinical Significance	Summary of Data/Rationale for Risk	Mitigation Strategy
	Study Intervention(s)	
Hepatotoxicity	In 2001, GSK routine monitoring of spontaneous ADRs identified an increased number of reports of elevated liver enzymes in patients receiving low dose albendazole and reports of hepatitis and jaundice in patients receiving high dose albendazole. Higher doses of albendazole are used to treat systemic helminth infections for longer periods compared to the low dose, short treatment durations required for intestinal helminth infections in the OTC environment. A cumulative review of hepatic events was conducted to further evaluate the nature of these events and to determine whether GSK's CSI adequately reflected these adverse events. Following the review of the available data, GSK concluded that there was sufficient evidence to suspect albendazole as causing hepatic events; with low dose albendazole causing	This study will not include participants with abnormal liver function test results (transaminases). Discontinuation of study intervention in the best interest of the participant for abnormal liver tests at the investigator discretion, when liver parameter falls outside the pre-defined clinically acceptable values. If any participant has clinically significant abnormal liver function analysis during the study, in such case participant may be discontinued for specific period at the investigator discretion. The decision to continue/discontinue such participants will be based on investigator's decision.

Protocol Version No. 1.0

Detential Diely of Clinian	Summaria of	Mitigation Stratogy		

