Potential Risk of Clinical	Summary of Data/Rationale for Risk	Mitigation Strategy		
Significance	Data/Kationale for Kisk			
	elevation of liver enzymes and the high dose use causing hepatitis. The CSI for POM albendazole global data sheet (GDS) was therefore updated to include these events in the Adverse Reactions section as well as appropriate warnings in the Dosing and Administration and Warnings and Precautions sections			
Exposure during pregnancy	Pre-Clinical Data in common with other benzimidazole compounds, administration of albendazole to pregnant animals can cause abnormalities of foetal development, including increased embryo resorption, soft tissue malformation and skeletal deformities. This teratogenic and embryotoxic activity has led to the recommendation that albendazole must not be prescribed to females who are pregnant. Post marketing surveillance in 2012, the GSK POAP reviewed all relevant new data in a context specific manner with a view to providing an assessment on the use of albendazole (and mebendazole another benzimidazole, which is structurally and physiologically similar to albendazole) for the treatment of intestinal	Albendazole is contraindicated in pregnancy and should not be administered during pregnancy or in women thought to be pregnant. Pregnant women will not be included. Serum Pregnancy test for female participants will be done at the time of screening, prior to check-in of each period and at the end of the study (at the time of check-out of period IV). Pregnancy testing must be done even if the participant is menstruating at the time of the study visit. The study intervention may only be administered if the pregnancy test is negative. For female participants history of menstruation and use of contraceptive methods will be evaluated by trained study physician at the time of screening.		

Protocol Version No. 1.0

Potential Risk of Clinical	Summary of	Mitigation Strategy		
Significance	Data/Rationale for Risk	→ ·····• √		

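### Criterion 5.1(f) sets no contraception end date after the last dose; study completion under 4.4 can come about 24 h post-dose, when sulfoxide is still about 20% of peak (low risk, precautionary fix)

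*Protocol*

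**What the plan says.** Protocol 5.1(f) admits women surgically sterilised at least 6 months earlier, or otherwise: "If of childbearing potential is willing to use a suitable and effective double barrier contraceptive method or intra uterine device during the study". A negative serum pregnancy test is also required.

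Section 4.4 treats a participant as complete once all periods are done, "including the last scheduled procedure shown in the SoA (i.e. at the time of check-out of period IV"). On the timing of check-out, section 4.1 says participants "will continue to remain in the clinical facility for at least 24 hours after administration of the intervention in each period"; the notes to the schedule of activities put it on the morning of Day 2.

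Appendix 4 (section 10.4) has contraceptive guidance in its title, but defines only who is and is not of childbearing potential. It gives no duration.

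On the hazard, Table 3 in section 2.3 describes abnormal foetal development in animals and adds: "This teratogenic and embryotoxic activity has led to the recommendation that albendazole must not be prescribed to females who are pregnant". The same section says of the label risks as a whole: "The likelihood of these risks in a healthy population receiving a single dose is therefore expected to be low".

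Pregnancy tests are scheduled at screening, before each check-in and at period IV check-out (8.3.5). Section 10.3.5.5 requires the investigator to report an SAE arising from a post-study pregnancy if it is judged reasonably related to the study intervention.

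**The concern.** The contraception requirement lasts as long as the study does, so its end date depends on how the study's end is defined. Under 4.4 a woman relying on a double-barrier method may stop on the morning after her last dose and still have complied fully. Section 2.2 calls the sulfoxide the main metabolite and the active moiety for systemic infections, and gives it a much longer half-life than the parent. A drug contraindicated in pregnancy would therefore still be represented in the circulation by that metabolite when the requirement lapses.

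The last scheduled pregnancy test falls at the same check-out. It cannot detect a conception after discharge, and neither it nor the reporting duty in 10.3.5.5 prevents one. What is at stake is a short interval of avoidable exposure. No estimate or test in the bioequivalence analysis depends on it.

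**Working it through.** The documents state no residual-exposure figure, so there is none to reproduce.

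**Inputs (protocol 2.2 and 4.1).** Peak times: "Peak concentrations are achieved for albendazole approximately 2 hours after dose, and for albendazole sulfoxide approximately 4 hours after dose". Half-life: it "is approximately 1.5 hours and for albendazole sulfoxide 8.5 hours". Check-out: 24 h after dosing, the earliest allowed.

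**Formula.** Assuming mono-exponential decline from the peak, the fraction of peak left at time t is 0.5^((t − Tmax)/t½).

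**At 24 h after the last dose**
- Parent: 0.5^((24 − 2)/1.5) = 0.5^14.67 = 0.000038, about 0.004% of peak.
- Sulfoxide: 0.5^((24 − 4)/8.5) = 0.5^2.35 = 0.196, about 20% of peak.
- Sulfoxide at an assumed half-life of 6 h: 0.5^(20/6) = 0.099, about 10%.
- Sulfoxide at an assumed half-life of 12 h: 0.5^(20/12) = 0.315, about 32%.

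A later check-out lowers these figures; at 26 h the sulfoxide value is 0.5^(22/8.5) = 16.6%.

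**Sulfoxide at two candidate end dates**

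| Time after last dose | t½ 8.5 h (protocol) | t½ 12 h (assumed) |
|---|---|---|
| 85 h | 0.5^(81/8.5) = 0.14% | 0.5^(81/12) = 0.93% |
| 168 h (7 days) | 0.5^(164/8.5) = 0.00016% | 0.5^(164/12) = 0.008% |

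Seven days spans 10 half-lives for any half-life up to 168/10 = 16.8 h. An 85 h limit spans 10 half-lives only if the half-life is no longer than the stated 8.5 h.

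**The competing rule in 7.3.** That section treats a participant as complete after 10 half-lives of the investigational product or the washout, whichever is shorter:
- Parent half-life: min(10 × 1.5, 168) = 15 h, which is before check-out and extends nothing.
- Sulfoxide half-life: min(10 × 8.5, 168) = 85 h, which adds (85 − 24)/24 = 2.5 days and largely closes the gap.

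Section 7.3 does not say which half-life applies. Section 4.4 also sets the overall end of study at the last participant's last procedure. That may fall later for some women, but it does not define a contraception period for an individual.

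**The case against.** The strongest objection is that the documents show no harm. Table 3 ties the embryo-foetal findings to giving albendazole, and nothing assigns them to the sulfoxide. For the parent drug the residue at check-out is about 0.004% of peak. A conception after discharge is also a different situation from dosing a pregnant woman. The Table 3 row further describes a review covering drug exposures in over 12,000 pregnant women (albendazole and mebendazole together), although the sponsor's safety board found the evidence insufficient to lift the contraindication in the over-the-counter setting. All of this stands, and it keeps the point at a precautionary level.

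Second, 7.3 may already carry the study to 85 h. That is possible, but a participant or site cannot derive a stop date from a rule that yields 15 h or 85 h depending on an unstated choice.

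Third, the consent form may state an end date, and pregnancy handling is deferred to an in-house procedure (8.4.5). Neither is available here, so the criticism is limited to the wording of the criterion.

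A reader might go further and infer one of two things the documents do not support:
- **That the 20% residue is itself a demonstrated foetal hazard.** The documents make no such link.
- **That a sizeable group of women is at risk.** The documents give no number of women or of double-barrier users. Even if up to half of the 70 participants used that method (an assumption, giving 0 to 35), this would not be a count at risk. Only a woman who both stops at discharge and conceives within the next few days is relevant. Sterilised women are unaffected, and users of an intrauterine device would in practice stay protected.

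**Conclusion.** The point holds as a gap in wording with a small, precautionary safety consequence. Criterion 5.1(f) gives no end date after the last dose. Read with 4.4, it lets contraception stop about 24 h post-dose, with parent drug essentially gone and sulfoxide at about 20% of peak (10% to 32% over the assumed half-lives). Section 7.3 conflicts with 4.4 and does not settle the matter.

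The percentages rest on typical peak times and half-lives, single-exponential decline and check-out at the 24 h minimum. The expected risk is low and the number of women concerned is unknown. Nothing here touches sample size, power, type I error or the bioequivalence conclusion. This is a cheap improvement, optional in priority.

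**What to change.** In 5.1(f), replace the closing words on duration with: *during the study and until at least 7 days after the last dose*. Leave the start of the requirement as it is; nothing here gives a reason to move it, and a start at screening could turn past use into an eligibility condition. Carry the same end date into the pregnancy row of Table 3 and, if it is not already there, into the consent form.

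Seven days is the protocol's own washout. Section 4.2 says the sampling and washout are designed so that "pre-dose concentrations are negligible in each subsequent period". On the calculation above it leaves less than 0.01% of peak sulfoxide for half-lives up to 12 h. A fixed number of days also removes any dependence on which completion rule, 4.4 or 7.3, is meant. Reconciling those two sections would be sensible editing, but the fix does not need it.

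The cost is a few words in two or three places and about (168 − 24)/24 = 6 more days of contraception for women of childbearing potential. There is no extra visit, test or blood sample.
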